1 Vital signs are collected at the Screening/Baseline, Week 3, and Week 24 visits and weekly in conjunction with study drug administration from Baseline through Week 24. Vital signs collected at in-clinic visits (Screening/Baseline, Week 3, Week 24) include systolic and diastolic pressure, respiratory rate, heart rate, temperature, and weight. Height is measured at Screening/Baseline Visit only. If significant weight change is reported or suspected at any point during the study, the SI may choose to collect an additional in-clinic weight at their discretion. During each weekly infusion, vital signs associated with the infusion (systolic and diastolic pressure, respiratory rate, and heart rate) are to be measured pre-infusion, 30 minutes (\pm 5 mins) after the start of infusion (SOI), 60 minutes after the SOI (\pm 10 mins), and 90 minutes (\pm 10 mins) after the SOI. If a participant requires a 90-minute infusion duration due to receiving more than 2 bags of study drug, an additional vital signs measurement is to be completed approximately 30 minutes (\pm 10 mins) after the end of the 90-minute infusion.

2 Clinical safety labs include hematology (CBC with differential), complete chemistry panel and urinalysis at Screening/Baseline, Week 3, and Week 24. Hb A1C will be included in labs at Screening/Baseline and Week 24. If labs are abnormal at Week 3, they may need to be repeated per investigator judgement. Serum pregnancy testing will occur in women of child-bearing potential at the Screening Visit and as necessary during the study. Pregnancy testing is only repeated as applicable if there is a concern for pregnancy. All urine samples must be collected prior to IP administration. Clinical safety labs may be drawn at the study site or obtained at a local site convenient for the participant. Clinical safety lab results obtained locally may be used to assess participant eligibility.

3 Infusion-related AEs are documented weekly in conjunction with study drug administration from Screening/Baseline through week 24

4 The weight collected at the Screening/ Baseline clinic visit will be used to calculate the participant's initial dose. The participant will remain on a stable dose until the next in-person visit when weight be collected, at which point the dose may be adjusted if the participant's weight has increased or decreased by 2kg. Additional information on dose adjustments is included in section 6.7.4 Dosing Changes.

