Document infusion-related adverse events ⁴	X ¹	X Weekly documentation of infusion-related adverse events.			
Columbia-Suicide Severity Rating Scale	X ¹	X		X	
Adjust Dose as Needed ⁵		X			
Administer/Dispense Study Drug ⁶	X Weekly infusions will continue through Week 24. Participants who join from OLE may do all infusions at home.				
Drug Accountability/Compliance ⁷	X Weekly infusions will continue through Week 24. Refer to the Pharmacy Manual, site policy, and GCP guidelines on drug accountability, compliance, and source documentation.				
Vital Status Determination ⁹				X	X

1 Participants who join from HEALEY ALS Platform Trial Regimen E RCT and/or OLE may leverage assessments completed during the last Platform Trial visit if the last Platform Trial visit is completed on the same day as EAP Screening visit. Only those assessments collected after obtaining written informed consent for the EAP may be used in such cases.

2 Vital signs are collected at Screening/Baseline, Week 3, and Week 24 visits and weekly in conjunction with study drug administration from Baseline through Week 24. Vital signs collected at in-clinic visits (Screening/ Baseline, Week 3, Week 24) include weight, systolic and diastolic pressure, respiratory rate, heart rate, and temperature. Height is measured at Screening/Baseline Visit only. If significant weight change is reported or suspected at any point during the study, the SI may choose to collect an additional in-clinic weight at their discretion. During each weekly infusion, vital signs associated with the infusion (systolic and diastolic pressure, respiratory rate, and heart rate) are to be measured pre-infusion, 30 minutes (± 5 mins) after the start of infusion (SOI), 60 minutes after the SOI (± 10 mins), and 90 minutes (± 10 mins) after the SOI. If a participant requires a 90-minute infusion duration due to receiving more than 2 bags of study drug an additional vital signs measurement is to be completed approximately 30 minutes (± 10 mins) after the end of the 90-minute infusion.

Mass General Brigham Institutional Review Board Intervention/Interaction Detailed Protocol

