6.4.3 Week 3 and Week 24 (or Early Termination)

Week 3 Visit (Day 21 \pm 3 days) and Week 24 (or early termination, Day 168 \pm 14 days) are in-person in-clinic visits that take place following the Screening/Baseline Visit. The following visit procedures (also outlined in the SOA) will be performed:

1. Measure vital signs including weight
2. Perform slow vital capacity (Week 24/ ET only)
3. Administer ALSFRS-R questionnaire
4. Collect ALSAQ-40 (Week 24/ ET only)
5. Collect blood samples for clinical safety labs including HbA1c and serum pregnancy testing for WOCBP (at investigator's discretion)
6. Collect blood samples for biomarker serum collection (Week 24/ ET only)
7. Review concomitant medications
8. Review adverse events
9. Administer the C-SSRS Since Last Visit questionnaire
10. Adjustment of dosing volume based on most recent weight measurement as necessary
11. Administer infusion of study drug
12. During each weekly infusion, vital signs associated with the infusion
13. Determine vital status (Week 24/ ET only)

6.4.4 Week 12

Week 12 (Day 84 \pm 7 days) is a remote telemedicine or telephone visit that takes place following the Screening/Baseline Visit. The following visit procedures (also outlined in the SOA) will be performed:

1. Administer ALSFRS-R questionnaire
2. Review concomitant medications
3. Review adverse events.

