4.1.1 Definitions, Derivations and Classifications

Definition of Baseline

The baseline value for all endpoints (i.e., laboratory parameters and vital signs) will be the last available value prior to the first dose of study treatment in Trehalose group, and the date of first study visit in historical control group.

Assessments taken on the same day as study treatment will be assumed to be before study treatment unless indicated to be obtained post-study treatment.

Definition of Day 1

Study Day 1 is defined as the first day of study treatment in Trehalose group, and the date of first study visit in historical control group. This will also be considered the reference start date.

Definition of Study Day

Study Day will be computed as follows:

- Study Day = (Date of event – Date of study day 1) + 1 if the date of the event is on or after the date of study day 1.
- Study Day = (Date of event – Date of study day 1) if the date of the event is prior to the date of the study day 1.

Derivations Involving Dates

The number of days between two dates, the date of interest and the reference date, will be calculated as (Date of event – Reference date) + 1 when the event date is on or after the reference date; or, as (Reference date – Date of event) + 1 when the event date is before the reference date. The resulting value is then converted to years, months, or weeks, as appropriate. Partial dates will be imputed before calculating the number of days (See Appendix 2 for partial or unknown date imputation rules).

Common Calculations

Change from baseline (CHG) will be calculated as:

$$\text{Change from baseline} = \text{Actual (observed) value at post baseline visit} - \text{baseline value}$$

Percent change from baseline (PCHG) will be calculated as:

$$\text{Percent change from baseline (\%)} = 100 * (\text{Change from baseline at post baseline visit} / \text{Baseline value})$$

If baseline is not available, the change from baseline and percent change from baseline will not be calculated and will remain missing.

Demographics

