4.1.2 Windowing, Unscheduled Visits and Repeat Test Results

All assessments collected at scheduled and unscheduled visits will be included in the by-participant data listings.

For Safety endpoints, the data will be analyzed according to the nominal visits except Baseline which is defined as last available value prior to the first dose of study treatment. The results collected at scheduled visits per

protocol will be included in the by-visit summary tables. For laboratory data analysis at the scheduled visits, central-laboratory values will (preferentially) be selected for a given visit; however, if there is no non-missing central-laboratory value available and there is a non-missing local-laboratory value collected at the visit, then a local-laboratory value will be used.

In addition, for Safety endpoints of laboratory data, vital signs and C-SSRS assessments, the last assessment during the post-baseline period will also be summarized using the analysis visit name “End of Treatment Period”, which is defined as the last measurement from all post-baseline visits including the unscheduled visits and early termination visit.

For Efficacy and Biomarker endpoints, the protocol defined visit windowing in Table 3 will be used to window the unscheduled visits or early termination visit to scheduled visit when it doesn’t exist. If unscheduled visits or early termination assessments fall in the same window, then select the assessment closest to the target assessment day. If there are two assessments that fall into a visit window and are equidistant from the target assessment day, then the later assessment will be selected.

Table 3 Analysis Visit Windows for Efficacy (ALSF-R, SVC, ALSAQ-40) and Biomarker

Analysis Visit	Nominal Day	Lower Limit	Upper Limit
Baseline	1	None	Time of first dose of study treatment
Week 3	22	19	25
Week 12	85	78	92
Week 24	169	155	183

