4.9.4 Vital Signs

Vital sign parameters to be summarized include Systolic Blood Pressure (mmHg), Diastolic Blood Pressure (mmHg), Heart Rate (beats/min), Respiratory rate (breaths/min), Temperature (C) and Weight (kg).

Vital signs will be summarized with descriptive statistics by visit and treatment cohort and overall. Descriptive statistics will be presented for results and change from baseline at each visit and time point where parameters were scheduled to be collected. For parameters Systolic Blood Pressure (mmHg), Diastolic Blood Pressure (mmHg), Heart Rate (beats/min), Respiratory rate (breaths/min) at infusion visits, the changes associated with the infusion from pre-dose to 30 mins post start of infusion (SOI), 60 minutes post the SOI, 90 minutes post the SOI, and 30 minutes post end of infusion (EOI) if collected will also be summarized.

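### The End of Treatment Period value for vital signs has no infusion time-point limit, so read literally it pools post-infusion and non-infusion readings against a pre-dose baseline

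*SAP*

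**What the plan says.** - **End of Treatment Period (SAP 4.1.2).** For laboratory data, vital signs and C-SSRS, the plan adds an analysis visit of this name, "which is defined as the last measurement from all post-baseline visits including the unscheduled visits and early termination visit". It sets no pre-dose or time-point condition. The only rule in that section for choosing between assessments in the same window (closest to the target day) covers efficacy and biomarker endpoints.
- **Baseline (SAP 4.1.1).** The baseline value "will be the last available value prior to the first dose of study treatment in Trehalose group".
- **Vital-sign tables (SAP 4.9.4).** "Descriptive statistics will be presented for results and change from baseline at each visit and time point where parameters were scheduled to be collected". The same section separately summarises changes from pre-dose to each later reading of an infusion. It does not mention the End of Treatment Period.
- **Schedule of readings (Protocol, Schedule of Activities footnotes on vital signs).** At each infusion, "vital signs associated with the infusion (systolic and diastolic pressure, respiratory rate, and heart rate) are to be measured pre-infusion", then at 30 and 60 minutes after the start, "and 90 minutes (± 10 mins) after the SOI". Infusions of more than 2 bags have a further reading about 30 minutes after the end.
- **Last treatment visit (Protocol 6.4.3).** The procedure list shared by Week 3, Week 24 and early termination includes clinic vital signs with weight, a study drug infusion, and a separate item, "During each weekly infusion, vital signs associated with the infusion".

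**The concern.** A last-value rule is harmless when a visit yields one value, as it normally does for laboratory tests and the C-SSRS. An infusion visit yields four or five readings of blood pressure, heart rate and respiratory rate, and all but the first follow the start of the infusion. The SAP keeps post-dose readings out of baseline but does not keep them out of the end-of-treatment value.

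At stake is what the row means. Its change from baseline would be a pre-infusion to post-infusion contrast for some participants and a change between two non-infusion states for others. A reader could not tell how much of a mean change was acute. Two programmers could also produce different tables from the same text. Long-term safety is a stated objective and vital signs are a named safety endpoint (SAP 1.1). This is also the row whose definition expressly brings in unscheduled and early termination visits.

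**Working it through.** The plan gives no figure to reproduce. The check applies the 4.1.2 rule to the protocol's schedule.

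**Inputs**
- 25 infusions over 24 weeks (Protocol, Schedule of Activities).
- Infusion time 60 minutes, at most 70, for up to 2 bags; 90 minutes, at most 100, for more than 2 bags (Protocol 6.7.3).
- Last scheduled reading: 90 ± 10 minutes after the start for up to 2 bags; 30 ± 10 minutes after the end for more than 2 bags (Schedule of Activities footnotes).
- Half-life about 1.5 hours, i.e. 90 minutes (Protocol 6.7.8).
- An early termination visit may fall 28 ± 7 days after the last dose (Protocol 5.1).

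**Step 1. Is there an infusion at the end of treatment?** One at baseline plus one in each of Weeks 1 to 24 gives 1 + 24 = 25, so a participant treated on schedule is infused at Week 24.

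**Step 2. When is the last reading of an infusion visit taken?** Time after end of infusion = reading time after start − infusion duration.

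| Infusion | Last reading | Minutes after end |
|---|---|---|
| Up to 2 bags, 60 min | 80 to 100 min after start | 80 − 60 = 20 to 100 − 60 = 40 |
| Up to 2 bags, 70 min | 80 to 100 min after start | 80 − 70 = 10 to 100 − 70 = 30 |
| More than 2 bags, 90 to 100 min | 30 ± 10 min after end | 20 to 40 |

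On schedule, the last reading always follows the infusion, by 10 to 40 minutes.

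**Step 3. How close is that to exposure?** Assuming single-exponential decay, the fraction of the end-of-infusion level remaining is 0.5^(t/90). At 10 minutes this is 0.926 and at 40 minutes 0.735.

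**Step 4. What does a last visit without an infusion contribute?** An early termination visit held as early as 28 − 7 = 21 days after the last dose, with no infusion given, is 21 × 24 / 1.5 = 336 half-lives later. Essentially no drug remains.

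**Step 5. What does pooling do?** Let D be the mean change over time between non-infusion states, δ the mean acute shift at the last infusion reading, and p the share of participants whose last reading is post-infusion. If δ does not depend on which group a participant falls in, the row estimates D + pδ. Two cohorts with the same D and δ but different shares would differ by (p1 − p2)δ. The documents give neither δ nor p, so the size of the error cannot be computed from them.

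**Which parameters?** The infusion-associated set is systolic pressure, diastolic pressure, respiratory rate and heart rate. Temperature and weight are clinic-visit measurements only. Four of the six parameters in SAP 4.9.4 are therefore affected.

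**The case against.** The strongest reply is that visit and time point are separate dimensions. SAP 4.1 says outputs are presented by visit and time point as applicable, and 4.9.4 tabulates vital signs that way. The End of Treatment Period could then be the last record within each time point, leaving its pre-dose row purely pre-dose. The table shells sit in a separate Data Presentation Plan, which may settle the matter. This reading is possible, but nothing in the SAP applies it to this analysis visit, and the single last-measurement definition points the other way.

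Three stronger readings are tempting and are not supported:

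- *That long-term change in vital signs would be lost.* SAP 4.1.2 introduces the row as an addition to the nominal-visit tables. SAP 4.9.4 gives change from baseline at scheduled visits and time points, so Week 24 and the weekly pre-infusion rows still show it.
- *That completers always contribute acute readings and everyone else a non-infusion one.* A clinic visit and an infusion may share a day but need not (Schedule of Activities footnotes), and the Week 24 window is ±14 days. The early termination list itself includes an infusion. The mix is real, but the documents do not tie it to completion.
- *That the infused volume shows how large the distortion is.* The volume is 0.75 / 0.0905 = 8.29 mL/kg, but that is not a change in blood pressure or heart rate.

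It is also fair to say that this is a supplementary descriptive row in an expanded access protocol with no formal hypothesis testing (SAP 2), and that all readings are listed.

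**Conclusion.** The point holds as a defect in one definition. Read as written, SAP 4.1.2 selects a post-infusion value of four vital signs for anyone whose last visit includes an infusion, and a non-infusion value for anyone whose last visit does not, both against a pre-dose baseline. The timing of 10 to 40 minutes after the end of infusion assumes on-schedule infusions and readings. The 74% to 93% of drug level remaining (0.735 and 0.926 before rounding) also assumes single-exponential decay, and it describes exposure, not haemodynamic effect.

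The consequence is limited to the interpretability of one descriptive safety row. If there is no acute shift, the row is unharmed; if there is one, the row carries it in an unknown proportion. Efficacy, alpha, power and sample size are unaffected. It should be corrected because the correction is cheap and loses no information.

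**What to change.** In SAP 4.1.2, state that for systolic pressure, diastolic pressure, heart rate and respiratory rate the End of Treatment Period value is the last pre-infusion or non-infusion reading (clinic, unscheduled or early termination). Readings after the start of an infusion stay in the within-infusion change summary of 4.9.4. For clinic readings taken on an infusion day, say how they are placed relative to the infusion. The same-day convention already in 4.1.1 (assumed before treatment unless indicated otherwise) could be extended to them. Temperature and weight need no change.

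Alternatively, present the End of Treatment Period separately by time point and say so in 4.1.2 and 4.9.4.

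Either option costs one or two sentences in the SAP and one filter or grouping in the dataset program, with no new data. The matching table shell should be checked for agreement.

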5.1 Participant Discontinuation

Participants who early terminate from the study will be asked to be seen for an in-person Early Termination Visit and complete a Follow-Up Safety Call. The in-person Early Termination Visit should be scheduled as soon as possible after a participant early terminates. The Follow-Up Safety Call should be completed approximately 28 days after the last dose of study drug.

If the Early Termination Visit occurs approximately 28 ± 7 days after the last dose of study drug, the information for the Follow-Up Safety Call can be collected during the Early Termination Visit, and a separate Follow-Up Safety Call does not need to be completed. If the in-person Early Termination Visit does not occur within 28 ± 7 days of the last dose of study drug, the Follow-Up Safety Call should occur approximately 28 days after the last dose of study drug and the Early Termination Visit will be completed after the Follow-Up Safety Call.

If SLS-005 is stopped because of an adverse event or reaction, the investigator should assess if a visit is needed. Safety labs, vital signs, and medication updates and return should be considered. Follow-up should continue until the adverse event is resolved or stabilized as per the investigator's discretion. If the participant permanently discontinues drug due to an adverse event, then the specific/detailed reason for discontinuation because of an adverse event must be documented in the source documents and the EDC system, and the onset, resolution, severity, relationship, outcome, and treatment required for the adverse event should be recorded as well.

A participant may withdraw from the EAP at any time at his/her own request or may be withdrawn at any time at the discretion of the investigator or designee for safety, behavioral, compliance, or administrative reasons.

If a participant fails to return, or is unreachable, for a scheduled visit within the acceptable visit window, the site staff must make a reasonable attempt to contact the participant to determine the reason for missing the visit and collect any remaining drug.

The following actions must be taken if a participant fails to return to the clinic for a required visit: The site must attempt to contact the participant and reschedule the missed visit as soon as possible and counsel the participant on the importance of maintaining the assigned visit schedule and ascertain whether or not the participant wishes to and/or should continue in the EAP.

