Before a participant is deemed lost to follow-up, the investigator or designee must make every effort to regain contact with the participant (where possible, 3 telephone calls and, if necessary, a certified letter to the participant's last known mailing address or local equivalent methods). These contact attempts should be recorded in source documentation.

Should the participant continue to be unreachable, he/she will be considered as lost to follow-up and the site should document all attempts to contact. Their end of participation will be documented as the date of final communication in the opinion of the investigator. If a certified letter or email was sent, the date of the certified letter or email will apply.

Regardless of the circumstance, the detailed/specific reason for participant discontinuation must be recorded in the source documents and the EDC.

Documentation for discontinuation:

Detailed/specific reason for participant discontinuation

- Adverse Event
- Withdrawal of Consent by participant
- Investigator Decision
- Disease progression
- Protocol Terminated by Sponsor
- Lost to Follow-up
- Pregnancy
- Noncompliance
- Death
- Other

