2. STATISTICAL HYPOTHESES AND MULTIPLICITY ADJUSTMENT

No formal hypothesis testing will be conducted in this study. All analyses will be descriptive in nature. Any modeling that is performed will focus on parameter estimation. The Trehalose treated EAP participants will be compared to predicted placebo progression using historical controls, the p-values will be included to characterize associations and treatment effect but will mainly be used for the exploratory purpose and will not be adjusted for multiplicity.

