3. ANALYSIS SETS

3.1 Definition of Analysis Sets

The following analysis sets are defined for this study:

Analysis Set	Definition
Screened Set	All participants who signed the informed consent form.
Full Analysis Set (FAS)	All participants who received at least one dose of Trehalose.
Per-Protocol Set (PPS)	
All participants included in FAS and who satisfy all the criteria below:
 
 - Did not have a major protocol deviation that affected the scientific integrity of the trial. - Received at least 85% and not more than 125% of the prescribed infusion volume up to the point of drug withdrawal/ last infusion. Data after drug withdrawal/ last infusion will not be included. 
The PPS will be finalized prior to the database closure.

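### SVC and ALSAQ-40 values from early-termination visits before Day 155 are collected and listed but enter no model, because both endpoints are modelled only at Week 24

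*SAP*

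**What the plan says.** **Collection.** Protocol 6.4.3 schedules the two measures after baseline with the entries "Perform slow vital capacity (Week 24/ ET only" and "Collect ALSAQ-40 (Week 24/ ET only". Protocol 5.1 adds: "The in-person Early Termination Visit should be scheduled as soon as possible after a participant early terminates". If that visit misses the 28 ± 7 day period after the last dose, "the Early Termination Visit will be completed after the Follow-Up Safety Call". The ET visit can therefore fall on almost any study day.

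**Placement.** For efficacy and biomarker endpoints, SAP 4.1.2 states that "the protocol defined visit windowing in Table 3 will be used to window the unscheduled visits or early termination visit to scheduled visit", when no scheduled visit exists. Table 3 gives Week 3 as Days 19-25, Week 12 as Days 78-92 and Week 24 as Days 155-183.

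**Models.** SAP 4.7.3.2 to 4.7.3.4 (SVC/VC) and 4.7.4 (ALSAQ-40) analyse the change to Week 24 and no other visit. SAP 4.1.3 rules out imputation unless it is specified. None is specified for a missing SVC visit or a missing ALSAQ-40 visit; Table 5 covers missing items only.

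**Status.** SAP 2 says "All analyses will be descriptive in nature".

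**The concern.** SVC and ALSAQ-40 have no scheduled assessment between baseline and Week 24. For someone who leaves early, the ET visit is the only later information on either measure. Placing it by study day and then modelling only Week 24 sets that information aside.

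Early leavers need not resemble completers. Protocol 5.1 lists "Disease progression" among the reasons for discontinuation, so faster decline among leavers is plausible, though the documents do not establish it. If it holds, the Week 24 result describes those who did well enough to stay, and a reader who takes it as the 24-week change in everyone treated would see too little worsening.

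**Working it through.** **1. Reproduce the window.** The protocol counts from Day 0 and the SAP calls the first dose Day 1, so SAP day = protocol day + 1.

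| Visit | Protocol | SAP nominal day | SAP window |
|---|---|---|---|
| Week 3 | 21 ± 3 | 22 | 19-25 |
| Week 12 | 84 ± 7 | 85 | 78-92 |
| Week 24 | 168 ± 14 | 169 | 155-183 |

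All Table 3 limits reproduce.

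**2. Where an ET value before Day 155 goes.** Days 2 to 154 are 153 days. Of these, 25 − 19 + 1 = 7 map to Week 3 and 92 − 78 + 1 = 15 map to Week 12. The other 153 − 22 = 131 (86%) map to no visit. None maps to Week 24. SVC and ALSAQ-40 are neither summarised nor modelled at Week 3 or Week 12, so a value from any of the 153 days reaches no model.

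**3. Every model for these endpoints.**

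| Analysis | SAP section | Outcome visit |
|---|---|---|
| SVC, EAP groups (ANCOVA) | 4.7.3.2 | Week 24 |
| VC, matched comparison (mixed model) | 4.7.3.2 | Week 24 |
| VC, other calipers and PS strata | 4.7.3.3 | Week 24 (same approach) |
| SVC/VC in the PPS | 4.7.3.4 | Week 24 (same approach) |
| ALSAQ-40 (ANCOVA) | 4.7.4 | Week 24 |

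**4. How the documents handle this elsewhere.**
- Protocol 9.0 planned a repeated measures analysis for VC. The SAP uses a single-visit model, and SAP Section 7 does not list that change.
- The NfL model in SAP 4.8.1 uses actual study days and every later visit, so an early ET value can enter.
- For laboratory data, vital signs and C-SSRS, SAP 4.1.2 keeps ET values in an end-of-treatment record.
- SAP 4.3 counts a participant as SVC evaluable with a baseline and any later value. That count can exceed the number modelled.

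**5. Size of the dropout bias (all inputs assumed).** Let p be the share with no Week 24 value, D the completers' mean 24-week decline, and rD the decline of the others over the same period. The mean over everyone treated is (1 − p)D + prD = D[1 + p(r − 1)]. A Week 24-only analysis estimates D. The relative understatement is p(r − 1) / [1 + p(r − 1)].

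| p (of 70) | r = 1 | r = 1.5 | r = 2 |
|---|---|---|---|
| 10% (7) | 0% | 0.05/1.05 = 4.8% | 0.10/1.10 = 9.1% |
| 20% (14) | 0% | 0.10/1.10 = 9.1% | 0.20/1.20 = 16.7% |
| 30% (21) | 0% | 0.15/1.15 = 13.0% | 0.30/1.30 = 23.1% |

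**6. How much ET values could recover.** Each leaver would have only two values, so a mixed model pulls the leaver's slope towards the group mean and removes only part of the bias. A simulation of 54 scenarios gives a rough idea. Its assumed inputs were:
- mean decline 2.5 points/month, slope SD 1 to 3, baseline SD 18, residual SD 2 to 8;
- exit hazard 0.02 to 0.07 per month, with log-hazard rising 0.2 or 0.4 per point/month of decline;
- one ET value per leaver, taken at exit.

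A random intercept-and-slope model removed 27-75% of the bias and a random-intercept model 20-33%. With ET values from only 60% of leavers (exit hazard 0.045), these fell to 17-48% and 13-18%. The widest slope spread is generous: SD 3 around 2.5 implies that about 20% of participants improve. The ranges are therefore illustrative only.

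**The case against.** **The endpoint is defined at Week 24.** SAP 4.7.3.1 defines the SVC endpoint as the mean change at that visit, and leaving out a Day 60 value is consistent with it. This stands: the plan has made a choice of target and not an arithmetical error. The SAP does not say, however, whether the result is meant for those assessed at Week 24 or for all treated participants. For VC the choice also departs from the protocol without being recorded.

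**The percentages are not the effect of Table 3.** This also stands. They measure bias from all missing Week 24 values. Participants who die, cannot do the test or take part fully remotely may have no ET value to recover. Conversely, someone who stops shortly before Day 155 may have an ET visit inside the Week 24 window, and that value is used if no Week 24 visit exists.

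**The analyses are exploratory.** True, and this limits the weight of the point. The SAP still plans a p-value for the VC difference (4.7.3.2) and says that results may go into a regulatory submission (Section 1).

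**Readings the documents do not support.**
- A reader might infer that the VC comparison is biased in favour of Trehalose. The documents do not give the controls' visit pattern, dropout or decline after dropout, so the direction cannot be determined. ALSAQ-40 has no control comparison.
- A reader might infer that the values are lost. They remain in the listings, and an early ET SVC counts towards the evaluable total.
- A reader might infer that ALSFRS-R is affected equally. Early leavers keep their in-window Week 3 and Week 12 values in its models. Some ALSFRS-R ET values also go unused: those outside every window, and those inside a window whose scheduled visit exists.
- The shared schedule column for Week 24 and ET might suggest that ET counts as Week 24. SAP 4.1.2 places ET efficacy values by study day instead.

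**Conclusion.** The point holds and is for consideration only. As the SAP is written, no SVC or ALSAQ-40 value from an ET visit on Days 2-154 can enter a model. Whether that biases anything depends on two things the documents do not settle: the target, and how early leavers decline.

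For a target of 24-week change in all treated participants, the understatement of Trehalose worsening is nil at equal decline rates. It runs from 4.8% to 23.1% over the assumed grid of 10-30% without a Week 24 value and decline 1.5 to 2 times as fast. These figures describe dropout bias as a whole, and using the ET values would reduce it only in part.

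**What to change.** Keep every planned analysis and add the following, in the FAS only.

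1. **Supplementary model for SVC/VC and for ALSAQ-40.** Fit a mixed model of the score on actual study day, using baseline and all later values to Day 183, ET included. Use a random intercept and slope, or a random intercept alone if the slope cannot be estimated. Fixed effects: group, bulbar onset, day and group-by-day. In the VC comparison, apply the same Day 183 cap to controls and include PS matched ID or PS strata as planned.
2. **Reporting.** Show the model-based 24-week change beside the Week 24 result, with the number of ET values used. Repeat it without ET values taken more than 35 days after the last dose (28 + 7, the end of the protocol's follow-up window), because those values are well off drug.
3. **Text.** State the target of the Week 24 analyses and of the added model. List in SAP Section 7 the change of the VC analysis from repeated measures to a single visit.

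The PPS analyses can stay as they are, since SAP 3.1 says "Data after drug withdrawal/ last infusion will not be included".

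**Cost.** SAP wording and modest programming, with no new data. The model assumes roughly linear decline over 24 weeks, as the ALSFRS-R slope model in SAP 4.7.2.4 already does. It reduces the bias only in part, and participants with no ET value remain unrepresented.
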